### **Performance**

- Change in MR from the 2-year follow-up data point to the 5-year follow-up as measured by TTE. Success will be defined as no change or any improvement in MR class as described in the American College of Cardiology/ American Heart Association (ACC/AHA) Guidelines

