#### **9.2.2.3 Performance**

The MR parameters left ventricle reverse remodeling (standard measurement points) and coaptation height will be tabulated using descriptive statistics. For the same parameters, a comparison with the clinical investigation 2010-040 2-year follow-up visit will be presented by absolute change and %-change. The changes in MR parameter values may also be analyzed graphically.

The Changes in NYHA classification when compared to the clinical investigation 2010-040 2-year follow-up visit will be summarized.

The number of subjects with recurrence of MR defined as changing of MR to moderate or severe according to ACC/AHA classification determined by TTE will be tabulated.

The percentage of subjects with recurrence of MR from 2-year follow-up visit will be calculated with their two-sided 95% CI.

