### **9.4 Missing, Unused and Spurious Data**

The handling of missing data will be detailed in the Statistical Analysis Plan.

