## **9.5 Datasets to Be Analyzed**

The Medtentia Annuloplasty Ring population (MAR population) consists of subjects, who underwent MV repair operation with successful MAR implantation in clinical investigation 2010-040. All analysis will be performed on the MAR population.

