4.2 Handling of missing values and other data conventions

Missing data will not be imputed.

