9.2.2.3 Performance

The MR parameters left ventricle reverse remodeling (standard measurement points) and coaptation height will be tabulated using descriptive statistics. For the same parameters, a comparison with the clinical investigation 2010-040 2-year follow-up visit will be presented by absolute change and %-change. The changes in MR parameter values may also be analyzed graphically.

The Changes in NYHA classification when compared to the clinical investigation 2010-040 2-year follow-up visit will be summarized.

The number of subjects with recurrence of MR defined as changing of MR to moderate or severe according to ACC/AHA classification determined by TTE will be tabulated.

STATISTICAL ANALYSIS PLAN

Sponsor:	Medtentia International Ltd Oy
Trial:	MAR2010-040FU5
Date:	27FEB2020

The percentage of subjects with recurrence of MR from 2-year follow-up visit will be calculated with their two-sided 95% CI, if applicable.

Any deviations from the planned analysis will be explained in the Statistical Analysis Report (SAR).

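### Does a conditional 95% CI for MR recurrence, with no written denominator, leave the result open to choice?

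*SAP*

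**What the plan says.** Protocol 9.2.2.3 states: "The percentage of subjects with recurrence of MR from 2-year follow-up visit will be calculated with their two-sided 95% CI". The SAP section with the same number repeats the sentence, but there the percentage "will be calculated with their two-sided 95% CI, if applicable". It does not say when the interval applies and names no method. It adds that departures from the planned analysis will be explained in the statistical analysis report.

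The endpoint in both documents is "recurrence of MR defined as changing of MR to moderate or severe according to ACC/AHA classification determined by TTE". The primary performance endpoint also needs a TTE: "Change in MR from the 2-year follow-up data point to the 5-year follow-up as measured by TTE" (Protocol 6.4.3). Its interval carries the same qualifier in both the protocol and the SAP (9.2.1.2).

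On missing data, Protocol 9.4 says "The handling of missing data will be detailed in the Statistical Analysis Plan". The whole of the SAP's answer, in 4.2, is "Missing data will not be imputed". The analysis set in Protocol 9.5 and SAP 4.1 "consists of subjects, who underwent MV repair operation with successful MAR implantation in clinical investigation 2010-040", so membership does not depend on attending the 5-year visit. Protocol 6.7 and SAP 3 give a maximum of 11, depending on who is located and agrees. Protocol 9.7 expects all 11.

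**The concern.** A SAP should not loosen a protocol requirement without giving a reason. Here it makes an unconditional interval conditional, with no rule. A result of 0% could then be printed without its upper limit and still comply with the SAP as written. Protocol 6.2 gives the aim as finding out whether the ring has kept MR trivial or mild. Recurrence answers that directly, and a bare 0% from at most 11 people can look more reassuring than it is. The SAP is dated 27FEB2020 and visits were planned for May to June 2019, so the qualifier was left open after planned data collection.

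The denominator looks open too. An analysis set defined by implantation suggests 11. No imputation suggests only those with a TTE. Once someone is absent, the two give different figures, and the primary proportion is affected more than recurrence.

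**Working it through.** **Inputs.** At most 11 subjects (Protocol 6.7, SAP 3). Reference intervals for 10/11 and 11/11 come from Protocol 3.2. The number without a 5-year TTE is not given; 1 to 3 is assumed below to show the range.

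**1. Reproduce the sponsor's own intervals.** The exact (Clopper-Pearson) 95% limits for x of n are:

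- lower = Beta quantile 0.025 with parameters (x, n−x+1), or 0 if x = 0
- upper = Beta quantile 0.975 with parameters (x+1, n−x), or 1 if x = n

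At x = n the lower limit reduces to 0.025^(1/n). For 11/11 this is 0.025^(1/11) = 0.715, giving 71.5–100. For 10/11 the quantiles give 58.7–99.8. Both match Protocol 3.2. Wilson (74.1–100 and 62.3–98.4) and Wald (100–100 and 73.9–107.9) do not. The earlier study therefore used the exact method, including at a boundary.

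**2. Can the interval ever be inapplicable?** At x = 0 the upper limit is 1 − 0.025^(1/n). For 0/11 this is 1 − 0.715 = 28.5%. For 1/11 the result is 9.1% (0.2–41.3), and for 2/11 it is 18.2% (2.3–51.8). No possible count prevents the calculation.

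**3. Size of the denominator question.** Each cell shows the estimate and exact 95% CI, with no recurrence seen and every assessed subject stable.

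| Assessed (assumed) | Recurrence, assessed only | Recurrence, over 11 | Primary, assessed only | Primary, over 11 |
|---|---|---|---|---|
| 11 | 0% (0–28.5) | 0% (0–28.5) | 100% (71.5–100) | 100% (71.5–100) |
| 10 | 0% (0–30.8) | 0% (0–28.5) | 100% (69.2–100) | 90.9% (58.7–99.8) |
| 9 | 0% (0–33.6) | 0% (0–28.5) | 100% (66.4–100) | 81.8% (48.2–97.7) |
| 8 | 0% (0–36.9) | 0% (0–28.5) | 100% (63.1–100) | 72.7% (39.0–94.0) |

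With one recurrence among nine assessed, recurrence is 1/9 = 11.1% (0.3–48.2) or 1/11 = 9.1% (0.2–41.3). Assessed-only gives the wider interval for recurrence, so it does not flatter that result.

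**4. Which reading does the plan produce?** To divide by 11 when nine were scanned, the other two must be given an outcome. They count as free of recurrence for that endpoint and as not successful for the primary: favourable in one, unfavourable in the other. Either way a value is assigned to a scan that was not done, which SAP 4.2 rules out. The analysis set says whose data are eligible; it does not supply a missing value. Read together, the sections lead to the number assessed. The 2-year side of the comparison raises no gap, since Protocol 3.2 reports 2-year MR status for all 11.

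**5. Would absences be hidden?** Disposition is presented for the implanted population (Protocol 9.6, SAP 4.3), which includes anyone who never attended. All-cause mortality has its own frequency table (9.2.2.1 in both). Required tests not done count as deviations (Protocol 11.10), and deviations are listed by subject (9.3 in both). Categorical results are given as counts and percentages (Protocol 9.1).

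**The case for a change.** The strongest case for a change is that the repair is nearly free: drop the qualifier, name the exact method, write one sentence on the denominator. Omitting the interval would comply with the SAP, so its sentence on explaining departures might not be triggered. Two absences would let the same data be reported as 100% or 81.8% on the primary endpoint.

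Part of this stands. The two documents differ, no criterion is given, and no sentence states the denominator.

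The rest is weaker. Protocol 9.1 covers departures from the protocol's own statistics section as well as from the SAP, so leaving out an interval required by Protocol 9.2.2.3 would call for justification in the study report, though only after the event and where appropriate. The SAP attaches the same qualifier to the cardiovascular admissions summary, where the protocol has none, which reads as a stock phrase and not as a decision about recurrence. The date of the SAP shows no fault: Protocol 9.2 asks only that it be final before the final analyses, and nothing indicates that results had been seen. The 81.8% figure requires the assignment of outcomes that SAP 4.2 excludes.

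A worst-case row counting each absence as a recurrence would give 9.1% (0.2–41.3), 18.2% (2.3–51.8) or 27.3% (6.0–61.0) for one, two or three absences. It would record a TTE-determined event in someone with no TTE, against the no-imputation rule. That is a debatable preference and does not repair a defect.

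**Conclusion.** No change follows. The qualifier and the unwritten denominator are gaps in detail on a descriptive secondary endpoint with no hypothesis test. An analyst who follows the plan reports the recurrence count and percentage among subjects with a TTE, together with an exact interval of the kind already used in the earlier study. If all 11 are assessed, the denominator question disappears and only the wording of the interval remains; at zero recurrences that interval is 0–28.5%. If 8 to 10 are assessed, the upper limit at zero recurrences is 36.9% to 30.8%, and the absences appear in the disposition table. This conclusion rests on two assumptions: that the analyst keeps to the exact method, which reproduces the earlier intervals, and that SAP 4.2 is applied to both TTE endpoints. Even if the interval were left out, the tabulated count with at most 11 subjects would let a reader compute it.

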9.2.2.4 Other

Number of subjects with re-operation or MV reintervention due MAR performance failure or malfunction will be summarized.

Quality of life scores as measured by the 15D©questionnaire will be summarized.

9.3 Reporting of Deviations

Any deviations will be collected to a deviation log by the study monitor and listed by subject in the final report.

4.7 Execution of statistical analysis

Statistical analysis will be performed by [REDACTED].

5 HARDWARE AND SOFTWARE

Statistical analysis, tables and subject data listings will be performed with SAS 9.4 for Windows.

6 REFERENCES

7 APPENDIX
